### Guidelines for Preparing a Research Protocol

#### Instructions:

- You do not need to complete this document if you are submitting an *Application for Exemption* or *Application for a Chart Review*.
- Do not use this template if:
  - Your study involves an FDA regulated product. In this case, use the *Clinical Trial Protocol Template*.
  - Your study has a protocol from a sponsor or cooperative group. In this case, use the *Protocol Plus*.
  - Your study is a registry or repository for data and/or samples, In this case, use *Protocol Template – Registry Studies* .
- If a section of this protocol is not applicable, please indicate such.
- Do not delete any of the text contained within this document.
- Please make sure to keep an electronic copy of this document. You will need to use it, if you make modifications in the future.
- Start by entering study information into the table above, according to these rules:
  - Protocol Title: Include the full protocol title as listed on the application.
  - Investigator: include the principal investigator's name as listed on the application form
  - Date Revised: Indicate the date at which the protocol was last revised
  - IRB Number: Indicate the assigned IRB number, when known. At initial submission, this row will be left blank.
- Once the table information is entered, proceed to page 2 and complete the rest of the form.

↓ Continue to next page to begin entering information about this study ↓

## 1. PREVIOUS STUDY HISTORY

Has this study ever been reviewed and rejected/disapproved by another IRB prior to submission to this IRB?

No  Yes – if yes, please explain:

## 2. BRIEF SUMMARY OF RESEARCH

- *The summary should be written in language intelligible to a moderately educated, non-scientific layperson.*
- *It should contain a clear statement of the rationale and hypothesis of your study, a concise description of the methodology, with an emphasis on what will happen to the subjects, and a discussion of the results.*
- *This section should be ½ page*

Gallstone disease affects over 20 million Americans. Among patients with gallbladder disease, the prevalence of choledocholithiasis (stones in the bile duct) is estimated to be 10-20%. Endoscopic retrograde cholangiopancreatography (ERCP) is considered the standard of care for removing stones in the bile duct utilizing a variety of conventional methods including biliary sphincterotomy, sphincteroplasty, extraction balloon, retrieval basket, and mechanical lithotripsy. After removal of stones from the bile duct, an occlusion cholangiogram is usually performed to confirm complete bile duct clearance. However, cholangiogram can miss residual stones in 11- 30% of cases - especially in the setting of a dilated bile duct, large stones, severe pneumobilia, juxtapapillary diverticulum, primary sclerosing cholangitis, and after lithotripsy (mechanical, electrohydraulic, or laser). The approach to patients with choledocholithiasis requires careful attention because missed bile duct stones can cause recurrent biliary symptoms, pancreatitis, cholangitis, and has significant cost implication with the need for repeat imaging and/or procedures.

## 3. INTRODUCTION/BACKGROUND MATERIAL/PRELIMINARY STUDIES AND SIGNIFICANCE

- *Describe and provide the results of previous work by yourself or others, including animal studies, laboratory studies, pilot studies, pre-clinical and/or clinical studies involving the compound or device to be studied.*
- *Include information as to why you are conducting the study and how the study differs from what has been previously researched, including what the knowledge gaps are.*
- *Describe the importance of the knowledge expected to result*

Peroral cholangioscopy (POC) provides direct visualization of the bile duct during ERCP and its benefits are well documented in numerous published studies. POC has been described for therapy of difficult to remove biliary stones utilizing electrohydraulic lithotripsy or laser lithotripsy with success rates of >90%. POC has also been used for evaluation of indeterminate filling defects and to assess for residual stones missed with cholangiogram. In a multicenter study evaluating POC for a variety of indications, 11% (7/66) of patients had bile duct stones identified only by POC that were missed on ERCP. In a study of patients with primary sclerosing cholangitis, 30% (7/23) of patients were found to have stones with POC that were missed with cholangiography. Takao et al. assessed residual bile duct stones found with POC in comparison to balloon-cholangiography; they found that 24% (26/108) of patients had residual stones seen with POC that were missed with balloon-cholangiography.

Although POC has been available for over thirty years, it has not become a widespread technique due to the fact that traditional cholangioscopes are fragile, cumbersome to use, and usually require two endoscopists to perform the procedure. A recent single operator semi-disposable cholangioscope, SpyGlass (Boston Scientific, Natick, Massachusetts), has addressed those concerns and has been shown in a studies to be a useful tool in visualizing the bile ducts and performing therapeutic maneuvers for biliary stones.

#### 4. OBJECTIVE(S)/SPECIFIC AIMS AND HYPOTHESES

- *A concise statement of the goal(s) of the current study.*
- *The rationale for and specific objectives of the study.*
- *The goals and the hypothesis to be tested should be stated.*

This is Prospective, single center study (One IRB, Two hospitals: North Shore University Hospital [NSUH] and Long-Island Jewish Medical Center [LIJ])

The primary goal of the study is to assess if POC will enhance the diagnostic yield in the detection of residual biliary stones that are missed during conventional ERCP. Residual bile duct stones can especially be seen in the setting of bile duct dilation, history of recurrent abnormal liver function tests, and after lithotripsy (mechanical, electrohydraulic, or laser). Missed biliary stones can lead to recurrent biliary symptoms, pancreatitis, and cholangitis. POC after conventional ERCP can be a useful diagnostic tool to confirm complete extraction of bile duct stones, and thus lead to decreased morbidity and decreased cost by avoiding unnecessary tests and repeat procedures.

#### Primary Endpoint:

The primary end point is to detect the presence of any stones seen during POC that were missed during conventional ERCP

**Secondary Endpoints:**

- a. Identify the change in management after finding stone on POC e.g. balloon sweep, stent placement, etc.

Identify the recurrence of biliary obstructive symptoms and/or imaging suggestive of recurrent (missed) stones which will be assessed with phone call at 3 months after procedure.

**5. RESOURCES AVAILABLE TO CONDUCT THE HUMAN RESEARCH**

- *Explain the feasibility of meeting recruitment goals of this project and demonstrate a potential for recruiting the required number of suitable subjects within the agreed recruitment period*
  - *How many potential subjects do you have access to?*
- *Describe your process to ensure that all persons assisting with the trial are adequately informed about the protocol and their trial related duties and functions*

Every year more than 150 patients undergo ERCP procedure in NSUH and LIJMC. Most of these patients will be eligible for participation in this study.

All personnel involved in the study are going to be part of the study and must have completed the necessary trainings for participation. All involved personnel will be informed of any changes in the protocol either through email or in person by the co-coordinator or the PI.

**6. RECRUITMENT METHODS**

- *Describe the source of potential subjects*
- *Describe the methods that will be used to identify potential subjects*
- *Describe any materials that will be used to recruit subjects. A copy of any advertisements (flyers, radio scripts, etc.) should be submitted along with the protocol.*
- *If monetary compensation is to be offered, this should be indicated in the protocol*

All consecutive patients with suspected or documented bile duct stones who satisfy eligibility criteria and who consent for participation in the study will be included in the study.

The source of potential subjects is the endoscopy suites at NSUH and at LIJMC. Majority of patients who were scheduled for standard of care ERCP procedure already have either documented or suspected presence of bile duct stones.

There are no advertisements for the recruitment as all the patients approached for consent are already scheduled for standard of care procedures.

There is no monetary compensation for participation in the study.

## 7. ELIGIBILITY CRITERIA

- *Describe the characteristics of the subject population, including their anticipated number, age, ranges, sex, ethnic background, and health status. Identify the criteria for inclusion or exclusion of any subpopulation.*
- *Explain the rationale for the involvement of special classes of subjects, such as fetuses, pregnant women, children, prisoners or other institutionalized individuals, or others who are likely to be vulnerable. You cannot include these populations in your research, unless you indicate such in the protocol*
- *Similarly, detail exclusionary criteria: age limits, special populations (minors, pregnant women, decisionally impaired), use of concomitant medications, subjects with other diseases, severity of illness, etc.*

### **Inclusion Criteria**

1. Patients above the age of 18.
2. Patient receiving ERCP as standard of care for suspected or documented choledocholithiasis as assessed by one or more of the following:
  1. Abnormal imaging on ultrasound, endoscopic ultrasound (EUS), CT scan, or MRCP suggestive of choledocholithiasis
  2. Clinical signs and symptoms suggestive of choledocholithiasis such as jaundice, abdominal pain, pruritis, pancreatitis, and/or cholangitis
  3. Abnormal liver function tests suggestive of choledocholithiasis (eg: serum bilirubin > 1.5 and/or elevated alkaline phosphatase levels)
3. In addition to one or more of the above inclusion criteria, patient must also satisfy one or more of the following:
  1. Mechanical lithotripsy, electrohydraulic lithotripsy, or laser lithotripsy performed for therapy of bile duct stones.
  2. Bile duct > 12mm on prior tests (any portion of duct)
  3. History of recurrent abnormal LFTs with negative cholangiogram.
  4. Positive EUS or MRCP for biliary stones with a negative cholangiogram

### **Exclusion criteria**

1. Patients less than 18 years of age.
2. Patients not undergoing ERCP as their standard of care.
3. Patients who had the following surgeries - Billroth II surgery, Roux-en-Y Gastric bypass surgery, and Whipple's surgery.

## 8. NUMBER OF SUBJECTS

- *Indicate the total number of subjects to be accrued locally. If applicable, distinguish between the number of subjects who are expected to be pre-screened, enrolled (consent obtained), randomized and complete the research procedures.*
- *If your study includes different cohorts, include the total number of subjects in each cohort.*
- *If this is multisite study, include total number of subjects across all sites.*

Number of patients: 100 who undergo POC in NSUH and in LIJMC

## 9. STUDY TIMELINES

- *Describe the duration of an individual's participation in the study*
- *Describe the duration anticipated to enroll all study subjects*
- *The estimated date of study completion*

The duration of the individual participation in the study is 3 months after their standard of care procedure for a phone follow-up.

Proposed duration of study: 1 year (enrollment 9 months + follow-up phone call at 3 months post-procedure).

Estimated date of study completion is December 2016.

## 10. ENDPOINTS

- *Describe the primary and secondary study endpoints*
- *Describe any primary or secondary safety endpoints*

### **Primary Endpoint:**

The primary end point is to detect the presence of any stones seen during POC that were missed during conventional ERCP

### **Secondary Endpoints:**

- b. Identify the change in management after finding stone on POC e.g. balloon sweep, stent placement, etc.
- c. Identify the recurrence of biliary obstructive symptoms and/or imaging suggestive of recurrent (missed) stones which will be assessed with phone call at 3 months after procedure.

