**Research procedures:**

1. Document the number of subjects who did and did not have any missed stones as identified by SpyGlass.
2. Document the number of stones missed if there were any.
3. Document clinical management after finding a stone.(eg: balloon sweep, lithotripsy, stent placement, etc.)
4. Follow-up contact with the participant  $\approx$ 3 months after the ERCP procedure if he/she is enrolled and had undergone cholangioscopy with Spyglass to document any recurrent stones/procedures/interventions.
5. Medical history will be obtained either directly from the patient or from the patient medical records which may also include questions about prior problems with medications used for sedation or other unusual medication reactions.
6. De-identified ERCP, endoscopic, EUS and SpyGlass images and/or video recordings may be collected for review, analysis, presentations and publications.

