#### **Endpoint Variables:**

1. Missed stones: Patients will be considered to have missed stones on conventional ERCP, if, after ERCP, one or more stones are seen with POC.
2. Change in management: any maneuver or combination of maneuvers performed after a missed stone (e.g. balloon extraction of stone, lithotripsy of stone, stent placement, etc.)
3. Recurrent stones within 3 months after POC, and documentation of cholecystectomy as applicable.

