#### **Statistical Methods:**

1. The proportion of subjects with missed stones will be estimated, along with the associated exact 95% binomial confidence interval.
2. Change in management will be described by calculating frequencies and percentages for each maneuver performed. This analysis will be restricted to subjects with missed stones.
3. The proportion of subjects with recurrent stones will be estimated, along with the associated exact 95% binomial confidence interval.

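### The 3-month recurrence endpoint includes imaging findings, but a phone call to the participant is the only source the plan names, and patients not reached have no outcome rule

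*Combined protocol and SAP*

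**What the plan says.** Sections 4 and 10 (Secondary Endpoints) both define recurrence as obstructive biliary symptoms and/or "imaging suggestive of recurrent (missed) stones which will be assessed with phone call at 3 months after procedure".

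The rest of the protocol describes the same single route:

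- Section 9 (Study Timelines): "The duration of the individual participation in the study is 3 months after their standard of care procedure for a phone follow-up".
- Section 11, Research procedures, item 4: one contact with the participant at about 3 months, if cholangioscopy (POC) was done, "to document any recurrent stones/procedures/interventions".
- Section 11, Research procedures, item 5, is the only place that names medical records as a source of clinical data, and it does so for history: "Medical history will be obtained either directly from the patient or from the patient medical records". Its example is past problems with sedation medication.

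Section 12 then narrows the variable and analyses it. Endpoint Variables, item 3, reads "Recurrent stones within 3 months after POC, and documentation of cholecystectomy as applicable". Statistical Methods, item 3, reads "The proportion of subjects with recurrent stones will be estimated, along with the associated exact 95% binomial confidence interval". Neither item gives a source document, a confirmation step, or a denominator for patients without follow-up data.

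Section 16 says when the call is not made, but only for patients whose procedure was not completed.

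**The concern.** Whether a scan suggested a stone is recorded in a radiology or endoscopy report. A patient may know that a scan was done without knowing what it showed, or may confuse a scan before the procedure with one after it. Error can therefore run in both directions. The analysed variable, recurrent stones, is harder for a patient to report correctly than symptoms are.

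A patient who is not reached supplies no outcome at all, and the plan does not say whether that patient is left out, counted as free of recurrence, or looked up.

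At stake is the one planned follow-up result, the proportion with recurrent stones. If events are missed, duct clearance after POC will look more complete than it was. The planned exact interval would not show this, because it reflects sampling error only.

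**Working it through.** **Inputs from the documents.** There are 100 patients with POC (Section 8) and 140 enrolled, with about 30% screen failure (Section 12, Sample Size Justification). The analysis is an exact binomial interval. The documents give no expected recurrence rate, reach rate or accuracy of patient report, so every value used for these below is an assumption.

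**Step 1. The plan's own figures.** For x events in n patients, the exact limits are the 0.025 quantile of Beta(x, n − x + 1) and the 0.975 quantile of Beta(x + 1, n − x). This gives:

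- 10/100: 4.9% to 17.6%
- 20/100: 12.7% to 29.2%
- 30/100: 21.2% to 40.0%

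All three match the table in Section 12. That table is for the primary endpoint; no precision is stated for recurrence.

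**Step 2. Is non-contact allowed for in the enrolment target?** 140 × 0.70 = 98, close to 100. The allowance is used up by screen failure, so nothing is set aside for loss to follow-up.

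**Step 3. Non-contact alone, with reports taken as accurate.** With x events among those reached and L patients not reached, the proportion in all 100 lies between x/100 and (x + L)/100.

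| Reached | Events | Estimate in those reached | Exact 95% CI | Possible proportion in all 100 |
|---|---|---|---|---|
| 85 | 4 | 4.7% | 1.3% to 11.6% | 4% to 19% |
| 90 | 9 | 10.0% | 4.7% to 18.1% | 9% to 19% |
| 80 | 8 | 10.0% | 4.4% to 18.8% | 8% to 28% |

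Each patient not reached widens the last column by one percentage point. That column carries no sampling error, and the interval beside it carries no uncertainty from non-contact.

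**Step 4. Non-contact and incomplete reporting together.** Let E be the true number of events in 100, a the share of events not reached, b the share of non-events not reached, and s the share of reached events that the patient reports. With no false reports, the expected estimate among those reached is

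E(1 − a)s / [E(1 − a) + (100 − E)(1 − b)].

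Taking b = 10% throughout:

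- E = 10, a = 10%, s = 100%: 9/90 = 10.0% (no bias)
- E = 10, a = 10%, s = 80%: 7.2/90 = 8.0%
- E = 10, a = 30%, s = 100%: 7/88 = 8.0%
- E = 10, a = 30%, s = 80%: 5.6/88 = 6.4%
- E = 10, a = 50%, s = 60%: 3/86 = 3.5%
- E = 5, a = 10%, s = 100%: 4.5/90 = 5.0% (no bias)
- E = 5, a = 50%, s = 60%: 1.5/88 = 1.7%

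The second line shows that the estimate falls with incomplete reporting even when loss is unrelated to outcome. False reports would push it back up. The formula shows what the plan leaves open; it does not predict the trial's result.

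**The case against.** The strongest reply is that the plan never says phone alone. Item 4 of the research procedures does not forbid confirming a reported event, and item 5 shows that study staff can use patient records. This is fair as far as it goes: the claim is about what the plan specifies, not what staff may do. But a route is specified, and record review for this outcome is not part of it. If charts are checked for some patients only, ascertainment becomes uneven.

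Second, the call does suit part of the endpoint. Symptoms are for the patient to report, and because of the and/or wording a patient scanned for symptoms already counts through the symptoms. Patients usually know of a repeat procedure. This stands for the endpoint as defined in Sections 4 and 10. It does less for the Section 12 variable, which counts recurrent stones and does not mention symptoms.

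Third, a reader might infer that patients who were readmitted or died drop out selectively, so that the estimate is certain to be too low. The documents do not support that. They give no figure for death, readmission or non-contact, they do not say that unreached patients are excluded, and a readmitted patient may still be reached at about 3 months. Section 4 names pancreatitis and cholangitis as consequences of missed stones, which makes selective loss plausible but does not establish it.

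Fourth, a reader might conclude that the study's case for lower morbidity and fewer repeat procedures is undermined. That also goes too far. Those statements in Section 4 are rationale, recurrence is not one of the two Specific Aims in Section 12, and without a comparator even complete follow-up could not show a reduction.

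**Conclusion.** The point holds in a limited form. As written, the plan would measure an imaging finding, and the stone-specific variable derived from it, through the participant's account, and it has no rule for participants who are not reached. Under-counting is the more likely direction, but false reports are possible, and the documents fix neither the size of the error nor any link between non-contact and outcome.

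On the assumption of 85 reached and 4 accurately reported events, non-contact alone leaves the proportion in the 100 patients anywhere from 4% to 19%, against a nominal interval of 1.3% to 11.6%. A different reach rate would change that range.

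The effect is confined to a descriptive secondary endpoint. The primary endpoint is observed during the procedure and is untouched. The change is worth making because it is cheap and replaces the stated method with a better one.

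**What to change.** 1. **Source.** In the Secondary Endpoints of Sections 4 and 10, and in Section 11, Research procedures, item 4, state that recurrence is assessed by phone call and by review of the NSUH and LIJ medical record at 3 months, for every POC subject, reached or not.
2. **Classification.** Record each imaging or stone recurrence as report-confirmed or patient-reported only, and show both. A reported event is then kept when an outside report cannot be obtained.
3. **Readmissions and deaths.** Count these as events only when the record shows recurrent stones or biliary obstruction. Report other deaths separately.
4. **Analysis.** In Section 12, Statistical Methods, item 3, use all POC subjects as the denominator. Give the numbers with phone plus record, record only, and neither. Add best- and worst-case bounds for those with neither, beside the exact interval.

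**Cost.** About 100 chart checks by existing staff in the hospitals' own records, the protocol wording, and confirmation that the signed authorisation covers outcome data. No procedure and no sample size changes. One gap remains: events treated elsewhere in patients who are not reached would still be missed.

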## 11. RESEARCH PROCEDURES

- *Include a detailed description of all procedures to be performed on the research subject and the schedule for each procedure.*
- *Include any screening procedures for eligibility and/or baseline diagnostic tests*
- *Include procedures being performed to monitor subjects for safety or minimize risks*
- *Include information about drug washout periods*
- *If drugs or biologics are being administered provide information on dosing and route of administration*
- *Clearly indicate which procedures are only being conducted for research purposes.*
- *If any specimens will be used for this research, explain whether they are being collected specifically for research purposes.*
- *Describe any source records that will be used to collect data about subjects*
- *Indicate the data to be collected, including long term follow-up*

All consecutive patients with suspected or documented choledocholithiasis who satisfy recruitment criteria outlined in Section 4 above and who consent for participation in the study will be included in the study.

